2.2 BACKGROUND

The NMDA receptor antagonist ketamine has shown promise as a novel, rapid-acting therapy for treatment-resistant depression. In 2006, Zarate and colleagues published an 18-patient randomized trial that demonstrated improved Hamilton Depression Rating Scale scores following 0.5 mg/kg ketamine infused over 40 minutes compared to placebo.¹⁷ Since then, this finding has been replicated multiple times, with a recent meta-analysis of 19 studies reporting that a single infusion of ketamine led to improved depressive symptoms compared to placebo at 4 hours and 24 hours.¹⁸ This is a much faster effect than oral antidepressants such as selective serotonin reuptake inhibitors, which take weeks to achieve maximum effect. Additional trials have demonstrated superiority of ketamine compared to active comparators such as midazolam.^{19,20}

The antidepressant properties of ketamine are potentially mediated by a sequence of events that lead to synaptogenesis and increased electroencephalogram (EEG) slow wave activity (SWA). Ketamine administration results in increased extracellular glutamate in the prefrontal cortex,²¹⁻²³ initiating a chain of events^{24,25} that leads to increased prefrontal synaptic density.²⁶ Enhanced synapse creation during wakefulness is followed by enhanced synapse pruning during subsequent sleep, which can be observed as SWA (1-4 Hz total EEG power) during non-rapid eye movement (NREM) sleep.²⁷ Low SWA during baseline sleep predicts ketamine responsiveness in depressed patients,²⁸ and increases in SWA following ketamine infusion correlate with symptom response.²⁹

Although ketamine achieves its antidepressant effect rapidly, the effect of a single bolus wanes over the first week, and strategies to achieve longer effects have been explored. A common strategy has been to use repeated intravenous ketamine boluses administered two or three times per week,^{30,31} although intranasal administration of the S enantiomer of ketamine has also been reported.³²⁻³⁴ Symptoms can be controlled for multiple weeks, but ongoing therapy is needed to sustain the effect.³⁵ An alternative strategy that eliminates the need for repeated dosing is to use a long-duration of infusion. Pilot studies have demonstrated that a 96-hour ketamine infusion titrated to a goal of 0.6 mg/kg/h leads to a rapid

reduction in depressive symptoms that can be sustained in a large majority of responders for up to 8 weeks after the end of infusion.^{36,37}

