5.5 STRATEGIES FOR RECRUITMENT AND RETENTION

Anticipated Patient Population – The target sample size will be 32 patients. Patients will be enrolled at a single site (BJH/Washington University School of Medicine). The expected accrual rate was estimated by examining characteristics (obtained via Epic Slicer Dicer at the population level only) of a retrospective cohort of patients who had non-emergent surgery at BJH between 1/1/2021 and 6/30/2021, had an ICU admission, and had an ICD grouper corresponding to depression documented in the diagnosis list or the past medical history. The query was limited to the cardiac, neurosurgery, and vascular services because many of the patients from other services (e.g., trauma, orthopedic) were suspected to have initially had emergent surgery followed by an ICU admission and then a non-emergent surgery. Exclusion criteria for the retrospective query included age < 18. During that 6-month time period, there were 307 patients who met these criteria (Figure 2). If we conservatively estimate that 20% of these patients enroll in the trial, that results in an accrual of 10 patients per month.

The gender, race and ethnicity, and age distributions are expected to follow the gender, race and ethnicity, and age distributions served by the Barnes-Jewish Hospital. These distributions were observed in the retrospective cohort seen in Figure 2. The anticipated characteristics of the study population are shown in Table 1.

[figure not shown]

Figure 2. Number of potentially eligible patients in a 6-month period.

Table 1. Anticipated Demographic Characteristics of the Study Population

Racial Categories	Ethnic Categories				Total	
	Not Hispanic or Latino		Hispanic or Latino			
	Female	Male	Female	Male		

American Indian/ Alaska Native	1	0	0	0	1
Asian	1	0	0	0	1
Native Hawaiian or Other Pacific Islander	0	0	0	0	0
Black or African American	2	2	0	0	4
White	13	11	1	1	26
More than One Race	0	0	0	0	0
Total	17	13	1	1	32

Recruitment Strategy – Patients will primarily be recruited at the Center for Preoperative Assessment and Planning (CPAP). Potentially eligible patients will be identified by screening the CPAP schedule. Patients identified via screening will be approached by telephone prior to their CPAP appointment or in person at CPAP.

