6.3 MEASURES TO MINIMIZE BIAS: RANDOMIZATION AND BLINDING

Randomization will occur postoperatively at the time of study medication preparation. Patients will be randomized in a 1:1 ratio to ketamine or normal saline placebo. Randomization will occur in blocks of 4. The randomization scheme will be held by the Investigational Drug Service.

Patients, research team members, and clinical staff (nurses, physicians) will be blinded to treatment allocation. To facilitate blinding, study medication for both the ketamine group and the control group will be delivered in 100 mL bags with identical appearance except for a unique study identifier.

Intentional unblinding of the clinical staff may occur in the case of serious adverse events if the attending physician feels knowledge of the treatment allocation will impact clinical decision making. The principal investigator will be notified of all instances of intentional unblinding.

Inadvertent unblinding may occur if the patient experiences side effects such as nystagmus, hallucinations, sedation, or hypertension/tachycardia. To detect inadvertent unblinding of the patient, we will ask the patient during the final study visit if they believe they received ketamine or placebo. To minimize the effects of inadvertent unblinding on study results, endpoints will be measured by study staff who were not present during the study medication infusion.

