At the baseline visit, the research team member will teach the participant how to use the Dreem headband for data collection. If the participant is recruited in the CPAP clinic, then the participant will take the Dreem headband home with them. They will be instructed to wear the headband and activate data collection while sleeping for one night. They will bring the headband back to the hospital with them

on the day of surgery. If the participant is recruited in the hospital, then the participant will wear the headband and activate data collection while sleeping the night following enrollment. The headband will be retrieved the following day.

Additional data collection using the Dreem headband will occur in preoperative holding, during the study medication infusion, the night following the study medication infusion, and the night following post-infusion day 1.

Postoperative Pain

Pain will be measured at the baseline visit and on post-infusion days 1, 2, 4, 7, and 14 using the visual analog scale. The participant will rate their pain at rest, when taking a deep breath, and with movement.

If the participant is discharged from the hospital before the day of the final study assessment, pain will be assessed over the telephone using an 11-point numeric rating scale at each remaining study time point. Pain will be rated at rest, when taking a deep breath, and with movement.

Postoperative Delirium

Delirium is assessed routinely by the ICU nurses using the Confusion Assessment Method for the ICU (CAM-ICU) once per shift. CAM-ICU scores between the day of the infusion and post-infusion day 5 will be retrieved from the electronic health record.

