9 STATISTICAL CONSIDERATIONS

9.1 STATISTICAL HYPOTHESES

The primary endpoints of this trial will be descriptive outcomes measuring feasibility rather than hypothesis-driven efficacy outcomes. The primary endpoints will include

- Primary Endpoint 1: Fraction of approached patients who enroll in the trial
- Primary Endpoint 2: Fraction of planned study medication infusions that are completed
- Primary Endpoint 3: Fraction of participants with MADRS scores available at all specified time points

The secondary endpoints of this trial will be efficacy outcomes, designed to test the following hypotheses with two-sided superiority comparisons. This feasibility trial is intended to provide estimates of effect sizes, but it will not be powered to test these hypotheses.

- Secondary Endpoint 1: Change in MADRS score between the preoperative assessment and post-infusion day 4
 - Null Hypothesis: The change in MADRS score will be the same in the ketamine group and in the control group.
 - Alternative Hypothesis: The change in MADRS score will be smaller in the ketamine group than in the control group.
- Secondary Endpoint 1: Delta sleep ratio on EEG obtained on the second night following the study medication infusion
 - Null Hypothesis: There will be no difference in delta sleep ratio between the ketamine group and the control group.
 - Alternative Hypothesis: The delta sleep ratio will be greater in the ketamine group compared to the control group.

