9.4 STATISTICAL ANALYSES

9.4.1 GENERAL APPROACH

For descriptive statistics, categorical data will be presented using frequency counts and percentages, normally distributed continuous data will be presented using means and standard deviations, and non-normally distributed continuous data will be presented using medians and interquartile ranges.

Normality will be assessed using visual analysis of histograms and using the Kolmogorov-Smirnov test. All inferential tests will be two-tailed, and p-values < 0.05 will be considered statistically significant.

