9.4.3 ANALYSIS OF THE SECONDARY ENDPOINT(S)

Secondary Endpoint 1:

For each randomized participant, the difference in MADRS score on post-infusion day 4 and at the preoperative baseline visit will be calculated. Participants with missing MADRS scores at either time point will be excluded. (No imputation of MADRS scores will be performed.)

The distribution of delta MADRS scores in the population will be assessed for normality using visual analysis of histograms and using the Kolmogorov-Smirnov test. If the delta MADRS scores are normally distributed, then the mean delta scores in the two groups will be compared using a two-sample t-test. If the delta MADRS scores are not normally distributed, then the median delta scores in the two groups will be compared using a Wilcoxon rank sum test.

Secondary Endpoint 2:

For each randomized participant, the EEG collected on the second night following the study medication infusion will be analyzed by an experienced sleep technician to identify sleep stages. Within each time

epoch captured, slow wave activity will be defined as the total power in the 1-4 Hz frequency band. The delta sleep ratio (DSR) will be defined as the ratio of SWA during the first non-rapid eye movement (NREM) epoch to SWA during the second NREM epoch.

The distribution of DSRs in the population will be assessed for normality using visual analysis of histograms and using the Kolmogorov-Smirnov test. If the DSRs are normally distributed, then the mean DSR in the two groups will be compared using a two-sample t-test. If the DSRs are not normally distributed, then the median DSR in the two groups will be compared using a Wilcoxon rank sum test.

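### The delta sleep ratio is compared between arms without adjusting for the pre-randomisation baseline night of EEG that the trial already records

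*Combined protocol and SAP*

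**What the plan says.** Section 9.4.3 defines the measure within a single night: "The delta sleep ratio (DSR) will be defined as the ratio of SWA during the first non-rapid eye movement (NREM) epoch" divided by SWA (slow wave activity, 1-4 Hz power) in the second. The night analysed there is the second after the infusion. The arms are then compared on that value alone: "If the DSRs are normally distributed, then the mean DSR in the two groups will be compared using a two-sample t-test", or by a Wilcoxon rank sum test if normality is rejected. No covariate and no confidence interval are named.

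Section 8.1 describes a preoperative recording. Of participants recruited in the clinic it says "They will be instructed to wear the headband and activate data collection while sleeping for one night"; those recruited in hospital wear the headband on the night after enrolment. The schedule of activities (section 1.3) marks EEG collection at screening. Section 6.3 places randomisation after surgery, when the study medication is prepared, so the baseline night precedes allocation.

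None of sections 9.4.1 to 9.4.9 uses the baseline night. The exploratory analyses in 9.4.9 are pain and lengths of stay. By contrast, Secondary Endpoint 1 in the same section is a change from the preoperative MADRS score.

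On size and purpose: "The target sample size will be 32 patients" and "Patients will be randomized in a 1:1 ratio to ketamine or normal saline placebo". Section 9.1 says of the secondary hypotheses that the trial is a source of effect-size estimates and "it will not be powered to test these hypotheses". Section 9.2 adds that the observed effect sizes and standard deviations will inform the sample size of the full-scale trial.

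**The concern.** Participants differ in DSR for reasons unrelated to treatment. If a person's DSR is at all stable from night to night, the baseline recording measures part of that difference. The planned test leaves all of it in the error term. With about 16 participants per arm the interval is wide to begin with, and the stated use of the estimate is to plan a larger trial. A covariate measured before randomisation, on the same device and already paid for in participant effort, is left out without a reason. The plan also forgoes the baseline-to-post correlation, which the designers of the full trial would need to decide whether to adjust.

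What is at stake is precision. Randomisation protects the unadjusted comparison from bias.

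**Working it through.** **The plan's own figures.** The documents give no effect size, SD, precision or power for DSR, so there is nothing to reproduce for this endpoint. The first precision figure in section 9.2, for enrolment, does reproduce: 1.96 × √(0.25 × 0.75 / 32) = 0.150, against ±0.15 stated.

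**Inputs from the documents.** Total 32 (sections 5.5 and 9.2); 1:1 allocation (6.3), hence n = 16 per arm; two-sided 5% level (9.4.1: "All inferential tests will be two-tailed, and p-values < 0.05 will be considered statistically significant"), hence a 95% interval.

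**Assumptions.** The correlation r between baseline-night and post-infusion DSR is not given; I show 0.3, 0.5 and 0.7. EEG is taken as complete. Results are in units of the between-participant SD of DSR on the scale analysed, so no SD has to be assumed.

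**Unadjusted comparison.** Half-width = t(0.975; 30 df) × √(2/n) = 2.0423 × √(2/16) = 2.0423 × 0.3536 = 0.722 SD.

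**Adjusted for baseline.** The residual SD is √(1 − r²) times the original, and one degree of freedom is lost. Half-width = t(0.975; 29 df) × √(2/16) × √(1 − r²) = 2.0452 × 0.3536 × √(1 − r²) = 0.7231 × √(1 − r²).

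| r (assumed) | √(1 − r²) | half-width (SD) | narrower than 0.722 by |
|---|---|---|---|
| 0 | 1.000 | 0.723 | −0.1% (slightly wider) |
| 0.3 | 0.954 | 0.690 | 4.5% |
| 0.5 | 0.866 | 0.626 | 13.3% |
| 0.7 | 0.714 | 0.516 | 28.5% |

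The residual variance falls by r², that is 9%, 25% and 49%. Those figures should not be read as the narrowing of the interval, which is the last column.

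**A refinement.** The table ignores chance imbalance in baseline between arms. With a normal covariate this inflates the variance on average by 1 + 1/28 (the mean of 1/χ² on 30 df is 1/28), so each adjusted half-width grows by √(1.0357) = 1.018. The three values become about 0.70, 0.64 and 0.53 SD. The gain at r = 0.3 is then about 3%; at 0.5 and 0.7 it stays material.

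**Fewer usable recordings.** With 13 per arm (assumed), the unadjusted half-width is 0.81 SD and the adjusted one at r = 0.3 is 0.77 SD, by the formulas of the table. The relative gain is about the same.

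**Which night.** The synopsis places the DSR on postoperative day 1, section 3 on post-infusion night 1, and sections 9.1 and 9.4.3 on the second night after the infusion. Section 8.1 records both the night after the infusion and the night after post-infusion day 1. The labels do not clearly name one night, and the model needs a single defined outcome.

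**The case against.** The strongest defence is that this is an unpowered secondary endpoint of a feasibility trial, that the planned test is valid, and that the benefit of adjusting is unknown. The baseline night may be at home for clinic recruits and the outcome night in hospital after surgery, so r may be low, and at r = 0.3 the gain is only a few per cent. All of this stands. It limits the size of the point, but it is not a reason to leave a recorded baseline unused when estimation is the stated purpose.

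A reader might go further and infer that DSR is the wrong marker and will miss ketamine's effect. Section 2.2 says that "increases in SWA following ketamine infusion correlate with symptom response", and a rise in SWA by the same factor k in both NREM periods cancels in the ratio, since (kA)/(kB) = A/B. The algebra is right, but the documents do not support the inference:

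- The objective (synopsis and section 3), the hypothesis (9.1) and the analysis (9.4.3) all target DSR. Section 3 gives its own reason for choosing it, a reported association with ketamine responsiveness. If DSR is unchanged, reporting no difference in DSR is correct.
- Nothing in the documents says that SWA rises equally in both periods. Under an assumed log-SD of 0.4 and a between-period correlation of 0.6, a 30% rise in both gives simulated power of about 5% for DSR and 44% for first-period SWA. A 30% rise in the first period only gives 49% and 44%. The ranking depends on an unknown pattern.
- Section 8.1 describes a consumer-grade, dry-electrode device. A within-night ratio removes night-to-night differences in signal gain; absolute power does not.

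A reader might also infer a serious loss of participants whose night has fewer than two NREM periods. Section 9.4.3 indeed gives no rule for a DSR that cannot be computed, but no document gives a rate, so the size of any loss is conjecture.

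**Conclusion.** The point holds as one of precision. Section 9.4.3 leaves a pre-randomisation EEG baseline out of the DSR comparison, and no other planned analysis uses it. At 16 per arm with complete data, adjustment would narrow the 95% interval from ±0.72 SD to about ±0.69, ±0.63 or ±0.52 SD at assumed correlations of 0.3, 0.5 or 0.7. The gain is negligible if the correlation is near zero. There is no bias in the planned comparison, and the recordings are kept, so it would be wrong to say that they are discarded. The documents do not support a conclusion that DSR misses the ketamine effect; absolute SWA is at most an optional exploratory analysis. The inconsistent naming of the DSR night is a separate defect that has to be settled first.

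**What to change.** In section 9.4.3, Secondary Endpoint 2:

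1. Replace the t-test or rank-sum choice with a linear model for post-infusion log DSR, with arm and baseline-night log DSR as terms. Report the adjusted ratio of geometric means with its 95% CI.
2. For planning the full trial, also report the SD of log DSR, the residual SD after adjustment, and the baseline-to-post correlation, noting that all three are imprecise at this sample size.
3. State a rule for a missing baseline, for example mean imputation of the covariate. Baseline is recorded before allocation, so a simple rule of this kind is acceptable.
4. Name one outcome night and use the same wording in the synopsis and sections 3, 9.1 and 9.4.3.

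The change should be made before anyone sees results by arm. It costs SAP wording, sleep staging of the baseline night by the same method as the outcome night, and one degree of freedom. No new data are needed. The return is small if home and hospital nights correlate weakly.

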9.4.4 SAFETY ANALYSES

Psychotomimetic Symptoms:

The BPRS four-item positive symptom subscale score and the CADSS-6 score will be calculated for each patient. The distribution of scores will be assessed for normality using visual analysis of histograms and using the Kolmogorov-Smirnov test. If the scores are normally distributed, then the mean score in the two groups will be compared using a two-sample t-test. If the scores are not normally distributed, then the median score in the two groups will be compared using a Wilcoxon rank sum test.

Clinical and Adverse Events Checklist:

The number of patients reporting each side effect during the study medication infusion will be determined. The incidence of each side effect will be compared between the two groups using a chi-square test (or using a Fisher exact test in the case of rare side effects).

Significant Hypertension during Infusion:

The number of patients experiencing a systolic blood pressure > 180 mmHg during the study medication infusion or receiving an antihypertensive medication during the infusion that is not on the patient's home medication list will be determined. The incidence of significant hypertension will be compared between the two groups using a chi-square test.

Tachycardia during Infusion:

The number of patients experiencing a heart rate > 100 beats per minute during the study medication infusion will be determined. The incidence of tachycardia will be compared between the two groups using a chi-square test.

Nausea and Vomiting:

The number of patients reporting nausea and vomiting will be determined. The incidence of nausea and vomiting will be compared between the two groups using a chi-square test.

Other adverse events will be coded and reported as described in section 8.3.

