2.3 RISK/BENEFIT ASSESSMENT

2.3.1 KNOWN POTENTIAL RISKS

The risks associated with ketamine have been observed in studies evaluating its use for general anesthesia (as a sole agent, for induction, or as a supplement to other agents), which generally involve higher doses than those to be used in this study.⁴⁶

Immediate risk of ketamine use may include

- Hypertension and tachycardia – These are common events at higher doses. Ketamine is contraindicated in patients for whom a significant elevation of blood pressure would constitute a serious hazard. (Of note, the low doses to be used in this study have not previously been associated with clinically significant changes in blood pressure or heart rate.³⁶)
- Psychotomimetic effects – These have occurred in approximately 12% of patients following anesthetic doses. These may range from pleasant dream-like states to vivid imagery, hallucinations, and emergence delirium.
- Respiratory depression – This is an uncommon event and may occur with overdosage or too rapid a rate of administration.
- Nystagmus, diplopia – These are common events. Rarely these may be associated with increases in intraocular pressure.
- Enhanced skeletal muscle tone
- Anorexia, nausea, vomiting
- Anaphylaxis

Long-range risks of ketamine include

- Pediatric neurotoxicity - Animal studies demonstrate increased neuronal apoptosis in developing juvenile brains and long-term cognitive deficits when used for longer than 3 hours.

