8.2 SAFETY AND OTHER ASSESSMENTS

Psychotomimetic Side Effects

Psychotomimetic effects will be quantified using the Brief Psychiatric Rating Scale (BPRS) four-item positive symptom subscale^{36,54} and using the modified 6-item Clinical Administered Dissociative State Scale (CADSS-6).⁵⁵ The BPRS four-item subscale yields a score between 4 (no symptoms) and 28 (extremely severe). The CADSS-6 yields a score between 0 (no symptoms) and 24 (severe symptoms). Both scales will be administered by a research team member midway through the study medication infusion (approximately 1-2 hours after the start of the bolus loading dose).

Clinical and Adverse Events Checklist

Additional side effects of ketamine will be detected using the Clinical and Adverse Events Checklist.⁵⁶ This checklist will be administered by a research team member midway through the study medication infusion (approximately 1-2 hours after the start of the bolus loading dose). The checklist will be repeated on post-infusion day 14 to monitor for resolution of any side effects.

Level of Sedation

Although the doses of ketamine used in this study are not expected to produce clinically significant sedation, patients will be monitored for sedation using the Richmond Agitation and Sedation Scale (RASS). RASS assessments will be conducted by the clinical bedside nurse per standard nursing protocols of the ICU. The nurse will also be asked to perform one extra RASS assessment at the end of the 10-minute bolus loading dose. If the RASS score is ever -2 or lower, the study medication will be held according to the protocol described in section 7.1.

Vital Signs during Study Medication Infusion

During the infusion, participants will receive vital sign monitoring per intensive care unit standard of care. This will include continuous telemetry, continuous pulse oximetry, and either intermittent

noninvasive blood pressure (at least hourly) or continuous invasive blood pressure (if an arterial catheter is present). Vital signs will be documented in the electronic health record by the clinical bedside nurse per unit standard of care. The research team will retrieve vital signs from the electronic health record.

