9.2 SAMPLE SIZE DETERMINATION

The sample size of 32 has been selected to allow the primary descriptive endpoints to be measured with acceptable levels of precision:

- Primary Endpoint 1: Fraction of approached patients who enroll in the trial

- Conservatively assuming that 25% of approached patients will enroll, then $n = 32$ patients will allow this proportion to be measured with a 95% confidence interval width of $\pm 15\%$:

$$95\%CI = \pm 1.96 \sqrt{\frac{p(1-p)}{n}} = \pm 1.96 \sqrt{\frac{(0.25)(0.75)}{32}} = \pm 0.15$$

- Primary Endpoint 2: Fraction of planned study medication infusions that are completed
 - If we assume that 90% of planned infusions are completed, then $n = 32$ patients will allow this proportion to be measured with a 95% confidence interval width of $\pm 10\%$:

$$95\%CI = \pm 1.96 \sqrt{\frac{p(1-p)}{n}} = \pm 1.96 \sqrt{\frac{(0.90)(0.10)}{32}} = \pm 0.10$$

- Primary Endpoint 3: Fraction of participants with MADRS scores available at all specified time points
 - If we assume that 95% of participants will have scores available at all specified time points, then $n = 32$ patients will allow this proportion to be measured with a 95% confidence interval width of $\pm 7\%$:

$$95\%CI = \pm 1.96 \sqrt{\frac{p(1-p)}{n}} = \pm 1.96 \sqrt{\frac{(0.95)(0.05)}{32}} = \pm 0.07$$

This sample size does not provide power to test the secondary endpoints for superiority. However, the observed values will be used to determine effect sizes, as well as standard deviations for the observed values. These quantities will inform the sample size calculation for the full-scale clinical trial. A minimum of 24-30 patients has previously been recommended for estimating effects sizes,^{61,62} so this feasibility trial should be large enough to provide the necessary estimates.

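### With 1 to 3 of 16 ketamine patients above the scale minimum, the planned BPRS and CADSS-6 median, quartile and rank test can all show nothing; add a count of affected patients by arm

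*Combined protocol and SAP*

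**What the plan says.** Section 8.2 uses two scales to quantify psychotomimetic effects, each given once, about midway through the infusion. The lowest possible score means no symptoms: 4 on the BPRS four-item positive symptom subscale (maximum 28) and 0 on the CADSS-6 (maximum 24).

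Section 9.4.4 compares mean scores by t-test if they look normal. Otherwise: "If the scores are not normally distributed, then the median score in the two groups will be compared using a Wilcoxon rank sum test". Section 9.4.1 settles the presentation: "non-normally distributed continuous data will be presented using medians and interquartile ranges". It also sets the test level: "All inferential tests will be two-tailed, and p-values < 0.05 will be considered statistically significant".

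The other named safety outcomes in 9.4.4 (checklist side effects, significant hypertension, tachycardia, nausea and vomiting) are reported as numbers of patients. The two psychotomimetic scales are not. Section 9.4.8 rules out presenting individual participant data.

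The only psychotomimetic rate in the protocol is in section 2.3.1: "These have occurred in approximately 12% of patients following anesthetic doses". Section 2.3.3 says the study regimen makes such effects less likely, without a figure.

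**The concern.** A patient without psychotomimetic symptoms scores exactly 4 or exactly 0. If most patients are in that position, the scores pile up at the minimum with a few raised values. Such data would fail the normality check and go down the median and Wilcoxon route. A median cannot move until about half the arm is affected, and an upper quartile cannot move until about a quarter is. A small number of affected ketamine patients could therefore leave the planned table reading 4 (4-4) against 4 (4-4), or 0 (0-0) against 0 (0-0), with a non-significant p-value.

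These two scales are the protocol's stated measure of psychotomimetic effects. The trial is meant to inform a full-scale trial, and section 6.3 names hallucinations as a way in which blinding may fail. How many patients were affected, and how badly, is what the next protocol will need to know.

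**Working it through.** **Inputs from the protocol.** Total sample 32 (section 9.2: "The sample size of 32 has been selected to allow the primary descriptive endpoints to be measured with acceptable levels of precision"). Allocation, section 6.3: "Patients will be randomized in a 1:1 ratio to ketamine or normal saline placebo". That gives 32/2 = 16 per arm. Two-sided 0.05 (9.4.1). Scale minima 4 and 0 (8.2).

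**Assumptions not in the protocol.** Unaffected patients score exactly the minimum; 0 of 16 saline patients score above it; the share p of ketamine patients above it is varied over a range.

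**The plan's own figure.** The sizing in 9.2 reproduces: 1.96 × √(0.25 × 0.75/32) = 0.150, the stated ±15%. It concerns enrolment. No rate, power or precision is stated for the BPRS or CADSS-6 comparison.

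**When the summaries move.** Let K be the number of 16 ketamine patients above the minimum.
- The median averages the 8th and 9th ordered scores, so it stays at the minimum for K ≤ 7 and leaves it from K = 8.
- The upper quartile (linear interpolation) stays at the minimum for K ≤ 3 and leaves it from K = 4.

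**When the rank test becomes significant.** The comparison is K of 16 against 0 of 16. The approximate p uses the tie-corrected normal approximation with continuity correction. The exact p is 2 × C(16,K)/C(32,K), capped at 1.

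| K | Median at minimum | Upper quartile at minimum | Approximate p | Exact p |
|---|---|---|---|---|
| 1 | yes | yes | 0.35 | 1.00 |
| 2 | yes | yes | 0.16 | 0.48 |
| 3 | yes | yes | 0.08 | 0.23 |
| 4 | yes | no | 0.039 | 0.10 |
| 5 | yes | no | 0.019 | 0.043 |

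So for K = 1, 2 or 3, patients are affected and all three planned outputs show nothing.

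**How often that happens.** With K ~ Binomial(16, p), the chance is P(1 ≤ K ≤ 3) = P(K ≤ 3) − P(K = 0), where P(K = 0) = (1 − p)^16. The last column is P(K ≤ 7).

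| p | P(K ≤ 3) | P(K = 0) | Blind spot | Median at minimum |
|---|---|---|---|---|
| 5% | 0.993 | 0.440 | 55% | >99.9% |
| 12% | 0.884 | 0.129 | 75% | 99.98% |
| 20% | 0.598 | 0.028 | 57% | 99.3% |
| 25% | 0.405 | 0.010 | 39% (0.39497 before rounding) | 97.3% |
| 40% | 0.065 | 0.0003 | 6% | 71.6% |
| 50% | 0.011 | <0.0001 | 1% | 40.2% |

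**Which branch applies.** In worked cases with 1 to 10 of 16 ketamine patients above the minimum and none on saline, the Kolmogorov-Smirnov check rejected normality every time. The Wilcoxon branch would normally be the one used.

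**What a count would show.** Take 2/16 against 0/16. The Wilson 95% limits are 0.035 to 0.360 and 0 to 0.194. The difference is 0.125. The Newcombe lower limit is 0.125 − √[(0.125 − 0.035)² + 0.194²] = −0.089, and the upper limit is 0.125 + (0.360 − 0.125) = 0.360. The result is 12.5 points, −9 to 36.

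**The case against.** **The pile-up at the minimum is assumed.** This stands. The protocol gives the bounds of the scales but no distribution at the study dose. A reader might take the 12% in section 2.3.1 as the expected share above the minimum. It is not: it describes clinical effects after anesthetic doses, not any raised score on a rating made mid-infusion at this dose. The table above therefore gives a range, and 12% is one point in it.

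**A Wilcoxon test compares ranks, not medians.** This also stands. A reader might infer from the wording of 9.4.4 that equal medians force a null result. They do not. Against 0 of 16, the test is significant from 4 affected patients by the normal approximation and from 5 by the exact calculation, with both medians still at the minimum. In simulation at 25% against 0% (raised scores drawn as 1 + Poisson(3), an assumption), its power was 58%, and in 55% of all trials it was significant with both medians at the minimum. The interquartile range also moves from 4 of 16.

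**A count does not rescue inference.** True. The Newcombe interval for 2/16 against 0/16 includes zero. In the same simulation a Fisher test on counts had 38% power against 58% for the approximate rank test, so there is no case for demoting the rank test.

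**Affected patients may appear elsewhere.** They may be recorded as adverse events under section 8.3.4 or in the checklist counts. But section 8.2 presents the checklist as covering further side effects and its items are not listed, so overlap cannot be assumed.

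**The safety monitor.** A reader might infer that the independent safety monitor would see only these medians. Section 10.1.6 says which safety outcomes the monitor reviews, not in what form, so that inference is unsupported.

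**Conclusion.** The point holds in a limited, conditional form. If fewer than half of the ketamine patients score above the minimum, both medians read as no symptoms. With 1 to 3 of 16 affected, the median, the upper quartile and the rank test all show nothing, and no count above the minimum is planned for these two scales. The chance of that is about 55%, 75%, 57% and 39% at assumed shares of 5%, 12%, 20% and 25%. It falls to about 6% at 40% and 1% at 50%. These figures rest on 16 per arm, unaffected patients exactly at the minimum, and none raised on saline.

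The documents do not support saying that the planned result will read as no symptoms, or that the test cannot detect a difference when medians are equal. This is a gap in reporting that is free to close. It is not an error that invalidates the safety analysis.

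**What to change.** In section 9.4.4, under psychotomimetic symptoms:

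1. Keep the Wilcoxon rank sum test, but describe it as a comparison of ranks between arms and drop the statement that medians are compared. State whether the p-value is exact or approximate, because with this many ties the two differ (0.48 against 0.16 for 2/16 versus 0/16).
2. Add, by arm and for each scale, the number and percentage scoring above the minimum (BPRS > 4, CADSS-6 > 0) and the maximum score.
3. Add the risk difference for scoring above the minimum, with a 95% interval suited to small counts, such as Newcombe's.

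The cost is a few lines of wording and one table. The data are already collected, and the sample size and visit schedule do not change.
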